Group Procedures. Group is organized for families to receive information about social communication, emotional regulation, play development, and behavioral challenges in toddler playgroups in a relaxed, supportive, child-friendly setting that provides the opportunity to talk with a professional and meet other parents. Group is designed to provide parents with resources and supports for their child through weekly small parent group meetings using a curriculum to help parents focus their attention on their child's developmental needs. Handouts with activities for the parents and children to participate in during the month will be provided and samples are included in the Appendix. Group is different than Individual because it does not provide individualized intervention, does not provide direct instruction to the parent in the home on how to implement strategies and supports, and does not ensure treatment fidelity or the level of intensity. Up to 12 families will attend each group, with a blend of children with early risk for ASD ranging in age from 12 to 24 months. The groups are guided by an interventionist from psychology or a related discipline and meet for 9 months during the intervention period and monthly follow-up sessions with parents through the child's 36 month birthday. Information is provided to families through discussion and handouts, answering questions, describing scenarios, and making suggestions. Little documentation on generalization of group education training for parents is available. Kaiser and colleagues concluded that while there was variability in the speed and consistency of learning that occurred by parents, it took an average of 20 individualized clinical sessions prior to generalized use of the procedures in the home setting. In a large-scale review of empirical studies of parent implemented interventions for young children with communication disorders, including ASD, Hancock and Kaiser identify generalization of the intervention strategies by parents into the home environment as key. Thus, we have designed Group to provide helpful information and support to families; however, we do not anticipate that families will generalize the use of intervention strategies to activities at home from the education meeting.

The playgroup will consist of children enrolled in this study as well as community volunteers. Community volunteer children will be typically developing. We will not collect any data on the volunteers and their parents/caregivers will be advised of the time commitment if they would like to participate. If a research staff member deems it appropriate, the community volunteer may be referred for services outside of the study.

Individual Procedures. Individual teaches parents how to support their child's communication, social, and play skills in everyday routines, activities, and places. The clinician meets with parents for 2 home visits per week for 9 months. Individual is organized by phases, beginning with the initial home visit, a month of program planning, 6 months of intervention implementation, and 2 months of generalization. The initial home visit is designed to provide an overview of Individual to the family and to discuss the importance of intensive intervention, defined as active and productive engagement for 20-25 hours per week for children with ASD. The program planning phase entails completing the SCERTS Assessment Process (SAP), which is a curricular-based assessment using parent report and observation for children with ASD 60 to identify goals and objectives for the child and teaching strategies and supports for the parents. The program planning phase is completed by mapping out which objectives will be targeted in which routines and activities to total 5 hours a day, 5 days a week. Some assessment forms are included in the Appendix, others have been added to the IRB Smartform. The parent who is the primary caregiver will be the focus of Individual training. If both the mother and father or an extended family member share caregiving, then they can participate as long as they can attend Individual sessions regularly and are available for the home observation. In the implementation phase, the 2 weekly sessions will include the following three components: 1) setting the stage to briefly review and revise the agenda for that visit and gather updates; 2) intervention implementation with the following steps: a) review the objective, b) use modeling, guided practice, or video review to teach the strategy, c) provide feedback to the parent, and d) problem solving and plan for next time; steps a-d are repeated for 3 to 5 activities per session; and 3) summarize plans for parent implementation between sessions and data collection using ESI Daily Intervention Log. During generalization, the clinician meets with the family in a variety of community settings to teach the parent how to implement strategies in new settings.

Measures/Handouts/Guides

Parent Questionnaires Completed Monthly from 12-36 Months
Baby Siblings Research Consortium Inventory History Form
Parent Questionnaires Completed Monthly every 6 Months from
12-36 Months
ESI Home and Community Activities Family Impact
Questionnaire
Family Resource Scale
Parenting Daily Hassles
Parenting Sense of Competence
Parenting Stress Index-Short Form
Intervention Planning and Monitoring Forms (Individual)
Routines-based Family Interview
SCERTS Assessment Process (SAP)—SAP Report, SAP
Observation, and SAP Summary Forms

ESI Weekly Intervention Log
Home Visit Notes
Building Support from the Bottom Up: Promoting Your Child's
Active Engagement
Keeping an Eye on Weekly Progress: How's it going? Where do
we go from here?
Home Observation Feedback Form
Fidelity of Delivery by Interventionist: Interventionist Fidelity Forms
(Individual & Group)
Interventionist Fidelity Form for Parent-Implemented
Intervention (Individual)
Interventionist Fidelity Form for Information, Education, &
Support (IES)
Fidelity of Receipt by Parent: Completed Weekly by Interventionist
& Parent from 12-21 months (Individual)
Reflection Questions on Weekly Progress
Caregiver Involvement Scale
Caregiver Diary
Fidelity of Enactment: Parent Implementation of Intervention
Strategies at Home (Individual& Group)
About Transactional Supports
Everyday Activities of Toddlers and Their Families: Making Every
Moment Count
Instructions for Home Observation from 12 to 36 months
Measure of Active Engagement and Transactional Support
(MAETS)
Identifying Priority Intervention Outcomes
Intervention Satisfaction Forms Completed by Parents (Individual &
Group)
ESI Family Evaluation Survey for Individual
ESI Family Evaluation Survey for Group

Fidelity and Program Evaluation Procedures

Three components of intervention fidelity—delivery, receipt, and enactment and parent satisfaction will be measured and are included in the Appendix 2. Fidelity of delivery will be measured bi-weekly for Individual and bimonthly for Group to monitor whether the clinician delivered or implemented the intervention to the parent as intended from a video of an intervention session. The intervention coordinators from FSU will rate the clinicians using the Clinician Fidelity Review Form for Individual or Group and give feedback on any deviations from the intervention procedures on an ongoing basis. Fidelity of receipt will be measured only during Individual by interventionist rating of the parent's receipt of information that week and ability to implement the strategies and supports that they are learning using the Clinician Reflect Questions filled out weekly by the interventionist, the Caregiver Diary filled out weekly by the parent to monitor the parent comfort and buy-in to the treatment, and the Caregiver Involvement Scale filled out weekly by the interventionist to rate parent comfort and buy in to the treatment. These measures were developed by UCLA and are used in the AIR-B network and

in the ESI ongoing RCT. The clinician will then make adjustments and give feedback to the parent on an ongoing basis. Fidelity of *enactment* will be measured for both Individual and Group from the monthly home observation using the MAETS to monitor whether the parent enacts the intervention strategies in natural situations when the clinician is not present. *Parent Satisfaction* in intervention will be measured using the Individual and Group Family Evaluation Survey. Each survey solicits information about the parent's satisfaction with many aspects of the intervention as well as their sense of competence in supporting their child's development.

Expected Impact

With the infrastructure available for the Emory ACE Center, in collaboration with the FSU Autism Institute, this new collaborative team will be able to implement a large-scale treatment study of one of the youngest samples of children with diagnostic features of ASD. The expected impact of this study will: 1) document improved outcomes for the youngest sample of children with ASD receiving a manualized, cost efficient, appropriate, and effective intervention that is implemented in community-based settings; and 2) substantiate that individualized intervention beginning by 12 months of age leads to better outcomes, providing evidence that early detection of autism is crucial to enable access to early intervention.

6. Statistical Analysis

Data Analyses and Power

Data Analytic Strategy. The main research aims and hypotheses will be analyzed using a series of mixed models, focusing on Growth Curve Modeling (GCM) and Random-Effects Regression (RER) as more powerful alternatives to repeated measures ANOVA, and estimates of effect sizes will be obtained. We anticipate that effect size estimates will be conservatively derived from simple inspection of observed differences in treatment versus control means divided by the appropriate standardizer (either the control standard deviation or the pooled standard deviation, depending upon whether the treatment is inducing group differences in variances or not). The research aims compare growth trajectories (or residualized change, or outcome only, depending on the dependent variable of interest) for children in the treatment and control groups. It is hypothesized that children receiving the Group plus Individual condition will show significantly faster growth trajectories or change on the MAETS, which will mediate social communication, autism symptoms, developmental level, and adaptive behavior outcomes. Unconditional models that vary in complexity will be used to determine the most parsimonious models for estimating growth in this sample. After fitting the overall model, we will perform fixed-effects contrasts to test for cross-sectional differences between the two groups at points along the curve. Aims 2 and 3 build upon these models to investigate potential mediator and moderator variables that may predict response to treatment. Moderator variables such as initial level of child or parent performance and measures of family functioning will be interacted with treatment group to investigate potential moderating relationships. To investigate potential mediators of treatment effectiveness such as MAETS, we will follow standard strategy for testing mediational effects in a multilevel design where fidelity is conceptualized as a level 1 mediator that can vary by time. Finally, we will consider the possibility that the mediated relation may be stronger in one subgroup than the other (moderated mediation), either because treatment fidelity is accomplished to a greater extent in one subgroup than another or because the link between treatment fidelity and outcome is stronger in one subgroup than another (e.g., treatment fidelity predicts outcome only in individuals with sufficient cognitive abilities). In addition to existing GCM/RER analyses, in synergy with Projects I & II we will repeat our analyses using Functional Data Analysis, a new approach that significantly improves both the detection of common features in trajectory shape as well as the identification of individual spurts or delays relative to the group. Project III will rely on the Data Management and Analysis Core for data storage, management, and transmission to NDAR.

Attrition Analyses. All analysis will be done using an intention to treat approach. That is, every subject in the study will be considered in the analysis as a member of the treatment group to which s/he was assigned. We will conduct a series of analyses to examine attrition and its potential effect on the results ⁶⁹, including examining the differential attrition rates for the two treatments and for child and parent characteristics of those completing and those who did not complete one or both treatment conditions, different definitions of dropout, different outcome measures, and treatment-correlated attrition. For the HLM analyses with multiple time points, missing data are not a concern, but differential attrition by treatment group would be. If differential attrition appeared to be a problem, then we would conduct multiple imputation of missing data ⁹⁵ to attempt to estimate the appropriate effect sizes and confidence intervals.

Power Analyses. Power for growth curve modeling was estimated using a power estimation program developed for HLM models 61. When estimating power in growth curve models, there are a number of factors that need to be considered. In addition to alpha level, number of subjects, and anticipated effect size, power can also vary as a function of the number of observations employed and the duration of the study. For these power analyses, we set alpha at .05 and we anticipated as few as 5 and as many as 25 observations per child (per measure). Additionally, we estimated that there would be approximately 10 times as much within person variability than between person variability (the ICC for the person level effect would be .10). Using these estimates, we anticipate that 92 subjects would give us a power=.90 to detect an effect of d=.50 (which corresponds to a medium effect) with five time points estimating linear change. For models testing treatment differences in the presence of quadratic change (with 15 or more assessments per child), power is .95. If attrition drops the sample size to 80 subjects, we will still have power equal to .86 to detect a medium-sized effect (with five assessments estimating linear change) and power=. 91 for those treatment differences tested in the presence of quadratic change. Thus, the minimum power to detect medium effects with 80 subjects is .86. We anticipate that the use of FDA and PACE will increase power.

7. Risks

Parents will be informed that at any time during their participation in this study, they will have the opportunity to refuse to participate in any procedures or withdraw from the study at any time without prejudice or effect on them and their child. The initial assessment portion of this study takes about 5 hours, there is a risk that a child may become bored or tired. To minimize fatigue, breaks will be taken whenever necessary. This amount of time is typical for an assessment with children. We will take breaks and can reschedule as necessary. Attempts will be made to stop an assessment and/or treatment if the child seems to be reacting negatively. If a child becomes unduly upset, the assessment and/or treatment will stop immediately and attempts made to comfort the child. A follow-up phone call to the parent will be made in order to determine that the child and parent are comfortable. Participants do not have to answer any questions that they are not comfortable with. They are free to ask questions at any time during the study. Steps taken to minimize the risk to confidentiality include: (1)

keeping all data containing personal information in a locked file cabinet in a locked office to which only the research coordinators have access; (2) assigning identification numbers to all participants for tabulation of data; and (3) using identification numbers on all tests, questionnaires, and videotapes shared with other network sites. Participants will be informed that they do not have to answer any questions that may cause them discomfort. We will be as flexible as possible in scheduling assessments, and make expected time commitments clear to parents at the beginning of the study. Referrals for other treatment will be made if necessary. We have developed a specialized Microsoft Access database with tables linked by an assigned identification code to enter all of the data that will be gathered for this study. The database is housed on a web server with encrypting and password protection in compliance with HIPPA regulations. It is necessary for the project to have identifying information, including names and addresses, since clinical reports are generated from the project. Because the database is stored on a HIPPA compliant server that is accessed over the internet, if the actual project computers were stolen, the user could not access the database, thus protecting the security and confidentiality of the records. Queries are designed so that only de-identified data using the identification code will be exported and used for data analysis. Video recordings will be stored on a secure server in a password protected program.

8. Adverse Event Reporting

The procedures to be used in the study have no known hazards and are comparable with assessment and treatment procedures that have been used in psychological research for decades in infants, toddlers, and adults. During clinical and home visits, a parent will remain with the child at all times. If a child expresses displeasure due to any cause, the session will be suspended. With parental permission, treatment and/or assessment will continue when the parent deems that the child is ready. The researchers, clinicians, and research assistants who interact with the children and families have a background in child development and thorough knowledge of all experimental procedures.

All information that is collected in connection with this study will remain confidential and will only be disclosed as required by U.S. or State law. Examples of information that we are legally required to disclose include abuse of a child or elderly person, or certain reportable diseases. Every foreseeable precaution to protect confidentiality will be taken. As in all research studies, the potential risk for a loss of confidentiality exists (i.e., computer viruses, computer hackers). However, every reasonable precautionary measure will be taken to protect confidentiality of all data. Computers will regularly be updated for virus protection.

9. Data and Safety Monitoring Plan

Although minimal risks are anticipated, a Data and Safety Monitoring Plan (DSMP) will be established and will be responsible for data and safety monitoring. The DSMP will include the PI, Project Coordinator, and the Family Resource Coordinator from each site and will be headed by the PI. The DSMP will include a monthly meeting. across-site DSMP members will meet every six months through teleconference for review of child and family progress and inspection of the reliability of assessment measures and treatment fidelity measures to ensure the validity and integrity of the data. If any adverse events are identified, an adverse event report will be provided to the IRB at Emory and FSU and the funding Institute and Center. If children show an extremely slow rate of progress or regression, parents will be encouraged to increase

community resources that are available in the same way as they would be in our clinic. Other treatments will be considered as covariates of treatment effects. Although this may make interpreting the data more difficult, it would be unethical to deny children more intense treatment because of our research.

This research project proposes to manage data using Emory Amazon Web Services (Emory AWS), which is an Emory customized implementation of the Amazon Web Services ondemand cloud infrastructure for high-performance computing, data storage, database management, data sharing and hosting. Emory AWS provides investigators with access to many of the key research computing services offered by AWS. Additional security and technical controls help ensure that data are protected from unauthorized use, and that data storage and processing are conducted in a standardized, secure and HIPAA-eligible environment.

When using Emory AWS from the Emory campus, traffic flows through the Emory core network to the AWS environment, ensuring secure data transmission. Account creation is limited to Emory-authorized users and accounts are password protected, ensuring secure data access. As part of the account creation process, Emory AWS provisions a set of virtual private cloud environments that are automatically set to an approved configuration limiting user privileges and access to data and services, with appropriate levels of security and minimal risk of variations. Data stored in AWS are automatically encrypted with automatic versioning, backup, and logging, ensuring data integrity. All AWS services enabled in Emory AWS have been assessed for potential risks by the Emory Information Security team. Where applicable, the teams have built out monitoring and remediation controls to check and ensure that accounts do not implement configurations that may have unintended consequences or move them to a state of non-compliance.

For example, all storage must be encrypted; if storage is configured to be unencrypted, the monitor will notify the account owner and unmount the storage. All of these processes are automated, providing a greater level of assurance around data security, access control, firewall rules, network configurations, and environment setups. To satisfy HIPAA regulations, Emory has entered into a Business Associate Agreement (BAA) with Amazon Web Services. As a result of these precautions, Emory AWS may be used to store, manage, process and analyze data, including Emory electronic protected health information (ePHI), for the purpose of human subjects research.

- 01. Abidin, R. R.(1995). *Parenting Stress Index, Third Edition: Professional Manual.* Odessa, FL: Psychological Assessment Resources, Inc.
- 03. American Speech-Language-Hearing Association [ASHA]. (2006). *Guidelines for Speech Language Pathologists in Diagnosis, Assessment, and Treatment of Autism Spectrum Disorders Across the Life Span* [Guidelines]. Available from www.asha.org/policy.

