The overarching goal of this research protocol is to identify the health and developmental implications for age of screening and age of entry into early intervention for children at risk of Autism Spectrum Disorder (ASD). With increased number of young children identified with ASD, there is a pressing need for evidence-based, manualized, cost-efficient treatments that are accessible to and feasibly implemented by parents within their natural environments in community-based settings. Additionally, significant disparities in diagnosis and treatment of ASD have been found in racial and ethnic minority populations thereby increasing the need for families from diverse cultural and socioeconomic backgrounds. The major objective of this research protocol is to directly compare two parent intervention conditions of Early Social Interaction (ESI) for 9 months on developmental trajectories of infants showing early risk for ASD. The control treatment is an information, education and support group (Group) offered weekly; the experimental treatment is a parent-implemented intervention (Individual) offered in 2 weekly individualized sessions to teach parents how to embed strategies that support social communication skills, emotional regulation, and transactional supports skills within everyday routines, activities, and places, in combination with Group. This protocol will recruit 92 parentinfant dyads at 12 months of age from both the high and low risk siblings being studied in the Emory Autism Center of Excellence Projects 1 and 2. High risk infants will screen positive on 2 of 4 screening measures indicating the presence of diagnostic features of ASD by 12 months of age. Low risk infants who screen positive on 2 of 3 screening measures at the 12 month visit will receive a subsequent home observation measure. Any children who screen positive on this measure will qualify for treatment. Families will be randomly assigned through the process of minimization to either Group or Group and Individual for 9 months. The specific aims of this investigation are: Aim 1) Effectiveness of Treatment – to compare the effectiveness of Group +Individual on developmental trajectories of social communication, autism symptoms, social visual engagement, developmental skills, and adaptive behavior, compared to Group alone; Aim 2) Mediators of Treatment – to determine whether growth trajectories of child active engagement and parent transactional support are mediators of response to intervention; and Aim 3) Moderators of Treatment – to identify individual child and family characteristics which predict response to intervention.

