In response to RFA-HD-12-195, this treatment project is designed to address two significant public health challenges- the need for validated, manualized treatments for young children with ASD that are cost-efficient and feasible for community-based implementation, and the need to reduce the age of entry into early intervention. The major objective is to directly compare two parent intervention conditions for 9 months: 1) an information, education and support group (Group) offered weekly, and 2) an individualized parent-implemented intervention (Individual) offered in 2 weekly sessions to teach parents how to embed strategies to support social communication skills within everyday routines, activities, and places. The Emory ACE Center will recruit 92 parent-infant dyads at 12 months of age from theboth high and low risk siblings being studied. Inclusion criteria for high risk infants will be a positive screen on 2 of 4screening measures indicating the presence of diagnostic features of ASD by 12 months of age. Inclusion criteria for low risk infants will be a positive screen on 2 of 4 screening measures indicating the presence of diagnostic features of ASD by 12 months of age. Families will be randomly assigned to either Group or Group +Individual for 9 months. Outcome measures of social communication, autism symptoms, developmental level, and adaptive behavior will be gathered every 6 months from 12 to 36 months of age to measure treatment and follow-up effects. Measures of parent transactional support and child active engagement will be collected monthly beginning at 12 months until 36 months of age to examine change in developmental trajectories.

This project is conceptualized as a series of research questions (RQ) for each specific aim to examine the effects of intervention on outcomes of toddlers with ASD. The specific aims and research questions are:

Aim 1. Effectiveness of Treatment: To compare the effects of Group alone to Group plus Individual implemented from 12 to 21 months of age on outcome measures of social communication skills, autism symptoms, developmental levels, and adaptive behavior from 12 to 36 months. Research will address specific questions with regard to whether there are: RQ1a) differences in growth trajectories from 12 to 36 months on social communication skills and autism symptoms, and RQ1b) differences in trajectories of developmental level and adaptive behavior from 12 to 36 months for children receiving

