SORF rating from the home observation of the parent engaged in interaction with the child in everyday activities (meals and snacks, caregiving, play with toys or objects, play with people, book sharing, and family chores. The ESAC and SORF were chosen because these are the only empirically-supported screening tools for ASD at this age. FSU has extensive experience conducting screening and diagnostic evaluations of infants and toddlers using these tools and will oversee selection of referrals for this study. For high-risk infants, the selection criterion for participation in this treatment study is a positive screen on 2 of the 4 autism-specific screening tools with one of those positive screens being a SORF. For low-risk infants, selection criteria for participation includes a positive screen on both SORF measures and one additional measure (e.g., 3 out of 4 measures). The purpose of this early treatment study is to contribute to the overarching aims of the Emory ACE Center to study risk and resilience in ASD. Therefore, we are targeting infants who are genetically at risk and who show early signs of autism and communication delay. Thus, we are casting a broader net than only children who will end up with a diagnosis of ASD but are selecting siblings who are at the highest risk for having ASD or a developmental delay.

Random Assignment of Participants to Experimental Groups. Children who meet the selection criteria and whose parents give consent to participate in the study will be given a computer-generated random assignment to one of two groups- Group plus Individual or Group alone. As a complement to random assignment, we will covary pretest variables that end up being correlated with the outcome variables, in our statistical analysis, if the groups are not equivalent on these variables. The diagnosticians for all measures and raters for intervention fidelity and treatment mediators will be kept blind to group assignment.

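### Pretest covariates enter the treatment comparison only if they turn out to be correlated with outcome and imbalanced between arms, so the adjustment set is chosen after outcomes are seen and balanced prognostic variables are left out

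*Combined protocol and SAP*

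**What the plan says.** The only rule for pretest covariates in the treatment comparison is in section 5, under Random Assignment of Participants to Experimental Groups: "we will covary pretest variables that end up being correlated with the outcome variables, in our statistical analysis, if the groups are not equivalent" on them. Both conditions must hold. No test, p-value, correlation size or standardised difference is given for either, and no candidate variables are listed.

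No other section supplies a covariate set:

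- Section 6, Data Analytic Strategy, names no baseline covariates for Aim 1. It uses initial level and family functioning as moderators. It lets the comparison be of "growth trajectories (or residualized change, or outcome only, depending on the dependent variable of interest", without assigning an outcome to each form, and adds: "we will perform fixed-effects contrasts to test for cross-sectional differences between the two groups at points along the curve".
- Section 9 mentions other treatments as covariates. Those are received during the study and are not pretest variables.
- Section 4 states the RQ1a target as "differences in growth trajectories from 12 to 36 months on social communication skills and autism symptoms".

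On allocation, the protocol summary says: "Families will be randomly assigned through the process of minimization to either Group or Group and Individual for 9 months". Section 5 says that eligible children "will be given a computer-generated random assignment to one of two groups- Group plus Individual or Group alone". No minimization factors are named.

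**The concern.** A rule of this kind has three consequences. The covariate set is settled only after outcomes are seen. It can differ between the five dependent-variable domains in section 5. And adjustment is withheld where the arms look balanced, although adjusting for a prognostic variable improves precision whether or not it is imbalanced. At stake are some power and the ability of a second analyst to reproduce the primary result from the plan.

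**Working it through.** **The plan's power figure.** Section 6 states that "92 subjects would give us a power=.90 to detect an effect of d=.50" with five time points, and .86 with 80 children. It does not give the sidedness, the scale of d, the slope variance or the study duration, so .90 can be neither confirmed nor shown wrong. The two figures agree with each other: (1.96 + 1.282) × √(80/92) = 3.023, and Φ(3.023 − 1.96) = .856. They are taken as given below.

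**Inputs.** From the documents: 92 children, d = .50, alpha .05. Assumed, because the documents are silent: two-sided testing, 1:1 allocation, the outcome correlation r of each pretest variable (.10 to .60), outcome correlation judged at p < .05, and five plausible imbalance cut-offs (p < .05, p < .20, standardised difference > .25, > .20, > .10). The model is a single continuous outcome under simple randomisation. It is an illustration, not the planned mixed model, and does not describe the four-category language phase.

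**Step 1: precision.** Power with constant adjustment ≈ Φ(d√(N/4)/√(1 − r²) − 1.96), with d√(N/4) = .50 × √23 = 2.398.

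- Unadjusted: Φ(2.398 − 1.96) = .67.
- r = .50: Φ(2.398/√.75 − 1.96) = Φ(.809) = .79 (simulated .78).

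At r = .50 the rule brings the variable in for 5, 20, 23, 34 and 63% of trials at the five cut-offs. A variable explaining a quarter of the variance is thus left out in 37 to 95% of trials. Simulated power:

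| r | Rule, range over cut-offs | Always adjusted |
|---|---|---|
| .10 | .66 | .66 |
| .30 | .66–.68 | .70 |
| .50 | .67–.74 | .78 |
| .60 | .67–.78 | .84 |

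If the variable is the 12-month outcome score, this table applies only to an outcome-only analysis. On a random-intercept reading, "the ICC for the person level effect would be .10" implies r = .10 between occasions of one measure, where the loss is nil.

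**Step 2: false positives.** Under the null, each fixed cut-off rejects in about .03 to .05 of trials.

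**Step 3: reproducibility.** With five pretest variables at r = .10/.30/.50 (inter-correlation .3/.3/.4), the selected set differs somewhere among the five cut-offs in about 33/95/98% of trials. Averaged over the ten pairs of cut-offs, two analysts disagree on p < .05 in:

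- about 2/8/12% of trials at d = .50, where unadjusted power is about .66;
- about 0.7/3.6/3.4% when the effect is raised to d = .68, so that unadjusted power is about .90 as the plan states.

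**Step 4: does the baseline score alone suffice as a fix?** With five variables at r = .30/.50, always adjusting for one gives power of about .70/.78. The rule at its loosest cut-off (> .10) gives about .72/.86, and all five always in gives about .74/.89. A prespecified list limited to the 12-month score could therefore do worse than some versions of the rule it replaces.

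**Step 5: minimization, if used.** Let the factors explain R² of the tested contrast and be left out of the model, and let s = √(1 − R²). At R² = .30, s = .837.

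- Type I error = 2Φ(−1.96/s) = .019.
- Power without the factors = Φ(1.282/s) = .937; with them = Φ(3.242/s − 1.96) = .972.
- From the stated .86, the same formulas give .902 and .953.

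Omitting the factors makes the test conservative but leaves power at or above the stated values. Factors that predict level only leave the slope test near .05 (simulated .046 and .052 at R² .10 and .30).

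**The case against.** The strongest defence is that the most prognostic baseline value, the 12-month outcome score, is already in the main analyses: it is the first occasion of a growth trajectory, and residualized change conditions on it whatever the balance. That stands. A reader might infer from the rule that baseline outcome data are discarded generally; the documents do not support this. The exposure is limited to any analysis in the outcome-only form, which section 6 permits without naming one, and to the other pretest variables.

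A reader might also infer an inflated false-positive rate. Fixed cut-offs do not produce one. Choosing the cut-off after seeing results could raise the error to about .05 to .09, depending on how wide the search is, but nothing in the plan says that this is intended.

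It is tempting to quote a 17% or 26% rate of conflicting conclusions. Those figures count any disagreement among all five cut-offs, at power about .66 and r = .30 or .50. They do not describe two analysts, or the plan's stated power.

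Finally, computer-generated random assignment is compatible with minimization, since a computer can run minimization with a random element. That is fair: the two descriptions need reconciling, but they do not prove a contradiction. The correlations are assumptions throughout. The gap in the wording does not depend on them.

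**Conclusion.** The point holds, as a minor one. Section 5 ties adjustment to an outcome correlation seen after the fact and to observed imbalance, and no other section repairs this. The likely loss runs from nothing at correlation .10 to about 4 to 12 power points at correlation .50 for a single omitted score (.78 less .74 or .66). Disagreement between two analysts with five candidate variables is roughly 2 to 12% at power about .66, and about 1 to 3.5% at the stated .90. These sizes rest on a single-outcome model and assumed correlations and cut-offs. The stated powers of .90 and .86 are not shown to be wrong, and omitting minimization factors would not take power below them.

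**What to change.** In section 5, delete both conditions. In section 6, list for each Aim 1 outcome, before outcomes are seen, a short set of baseline covariates to be used regardless of observed balance:

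- the 12-month score of that outcome, as a covariate in any outcome-only model and as the first occasion in growth models;
- the few other pretest variables expected on prior grounds to be prognostic, such as risk group;
- the minimization factors, if minimization is used.

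In growth models, enter the covariates other than the outcome score with covariate-by-time terms, because main effects alone do not change the standard error of the group-by-time contrast. Name any outcome to be analysed in outcome-only form. Reconcile the summary and section 5 on allocation and, if it is minimization, state its factors.

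The cost is analysis wording, since the 12-month scores are already collected and risk group and any minimization factors are known at allocation. The downside is a few degrees of freedom with 80 to 92 children. For example, three binary covariates add 3 + 3 = 6 fixed-effect terms with linear time, or 3 + 6 = 9 with quadratic time, so the list should stay short.
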